Gait Modification Treatments for Knee Pathology
NCT: 03116230
September 7, 2017

Study Protocol and Statistical Analysis Plan

Project Title. Analysis of Pain, Function, and Joint Mechanics in Response to Two Treatments for Knee Pathology

Purpose. The objective of this project proposal is to complete a longitudinal clinical study of a cutaneous stimulation device in a target population of subjects with knee pathology. This work will determine the longer-term effect of the intervention on pain/function, gait/muscle function, and patient comfort.

Scientific Rationale. Knee injuries and pathologies such as anterior cruciate ligament (ACL)/meniscus tears and knee osteoarthritis (OA) are prevalent musculoskeletal conditions that cause functional limitations, pain and disability affecting patient quality of life and healthcare cost. Individuals with knee injuries who had undergone a meniscectomy or ACL reconstruction surgery and knee OA patients exhibit significant alterations in lower extremity muscle patterns involved in gait, including a weakness in the quadriceps muscle. Over the long term, an impairment in muscle activity may result in a change in mechanical stress loading of a joint and have adverse effects on the knee joint, and research increasingly suggests that such alterations may be significant predictors of onset and progression of knee OA.

Clinical guidelines for management of knee OA and associated joint injuries recommend non-pharmacological conservative interventions such as physical therapy, use of braces, elastic wraps, electrical stimulation and taping. These interventions are commonly used to improve muscle strength, joint stability and mitigate pain. However, treatment is often discontinued because of time constraints and cost involved, and hence there are limited long-term improvements.

To address these limitations, we have developed a device which utilizes a novel design to activate deficient lower extremity muscles through the somatosensory system and cutaneous stimulation. This device exploits the cross modal plasticity of the somatosensory system that controls touch, pain and proprioception. By applying intermittent cutaneous stimulation to the thigh and shank through vibration, it may activate the mechanoreceptors in the leg and thereby induce improved muscle contraction and a functional response during walking. This study aims to assess the changes in gait patterns and pain/function resulting from the intermittent cutaneous stimulation of afferent nerves on the surface of the thigh and shank.

Focus. Using a cross-over study design, this study aims to assess the influence of the cutaneous stimulation device versus a commercially-available knee sleeve on pain, function, and knee joint mechanics.

Anticipated Impact. Knee injuries and disease cause substantial pain and disability, and their high prevalence necessitate simple interventions. Clinical guidelines for management of knee OA and associated joint injuries emphasize the importance of non-pharmacological conservative strategies. Gait modification through cutaneous stimulation may offer a low cost alternative to rehabilitation programs and current treatments to address pain, deficient muscle activation in knee OA and conditions related to development of the disease.

Methods. The objective of this study is to conduct a cross-over study to assess the influence of the cutaneous stimulation device versus a commercially-available knee sleeve. We will use a single-center, single-blind, randomized, crossover study design. Participants will be told only that we are comparing two types of treatment for their knee pain.

Interventions will include: (A) Control treatment consisting of an off-the-shelf neutral knee sleeve and (B) Active treatment consisting of the cutaneous stimulation device.

Individuals with prior ACL injury/surgery, meniscus injury/surgery, and/or physician-diagnosed medial compartment knee osteoarthritis will be recruited. The participants will be 18 years or older, and both males and females will be recruited. Individuals below the age of 18 years old are excluded as they may not have reached skeletal maturity. Knee pathology subjects may be recruited through direct referrals from clinicians in primary care, rheumatology, physical medicine and rehabilitation, physical therapy, radiology, and orthopedic surgery. The group has successfully used advertising flyers to recruit subjects and we will also employ these methods for knee pathology subjects.

Subjects will be telephone screened for inclusion criteria. If the subject meets the designated criteria, he/she will be scheduled to visit the gait lab and enrolled in the study. The procedures will take approximately 2-3 hours.

At baseline testing, eligible subjects will be randomized to receive either treatment A or B for the initial 4 weeks and will receive a gait test. After the 4 weeks, the assigned treatment will be removed and a second gait test performed, and the participants will receive no treatment for 2 weeks. Following this 2-week washout period, the second randomized treatment will be

assigned for a 4-week period and a gait test performed. At the end of the 4-week period, another gait test will be performed. For each subject, the trial will last for a total of 10 weeks.

During each treatment, subjects will maintain a daily wear log, pain diary, and medication usage. Subjects will record the number of hours of brace wear each day and will be instructed to wear the brace during the active part of the day (greatest number of gait cycles).

During gait testing, each subject may be asked to walk at a variety of speeds and perform activities of daily living. A motion capture system consisting of infrared cameras and small reflective balls (markers) attached to the subjects using small double sided stickers and force platforms embedded in the floor will be used estimate subjects kinematics and kinetics during gait following the point cluster method protocol and standard inverse kinetics calculations. Pressure sensors may also be used to provide a 2 dimensional map of the pressure distribution in the stance phase of gait. EMG may be used to provide information on muscle activation. Additionally, inertial sensors may be placed on the bodies of the subjects to measure their kinematics. The markers and sensors will be placed on the bodies so that they do not impede the subject's movements in any way. Moreover, these elements do not impart excessive force. Ideally, the subject will forget that they are wearing the system. The walkway in the laboratory is well lit and free of obstacles. Outdoor testing may occur in a selected outdoor location that is also safe and unobstructed. There is little to no risk to the subjects beyond the normal risks associated with walking.

Subjects will be asked to complete questionnaires regarding pain, function, and physical activity.

Statistical Analysis Plan. Paired two-tailed t-tests will be used to assess changes in patient-reported outcomes and joint loading parameters (e.g. peak knee flexion moment) with each treatment from pre-treatment control.

Results.

- Mean +/- SD KFM at baseline for all 38 subjects : 3.14 ± 1.31
- Mean +/- SD KOOS Pain at baseline for all 38 subjects 66.25 ± 13.4
- Mean +/- SD KOOS Function at baseline for all 38 subjects 72.31 ± 15.98
- Mean +/- SD KOOS Symptoms at baseline for all 38 subjects 59.8 ± 15.58
- Mean +/- SD *change* in KFM (%Bw*Ht) separately for Treatment A and Treatment B from control (and # of subjects analyzed for each). **For slow walking**

Treatment A mean +/- SD change in KFM (%Bw*Ht) relative to control= 0.197 ± 0.374

Treatment B mean +/- SD change in KFM (%Bw*Ht) relative to control= 0.018 ± 0.725

- Statistical test used to compare the KFM and the p-values from it (separate p-values for Tx A and Tx B vs. control)
- T-test Treatment A P=0.005
- T-test Treatment B P=0.64

- Mean +/- SD *change* in KOOS Pain separately for Treatment A and Treatment B from control (and # of subjects analyzed for each).

Treatment A mean +/- SD change in KOOS Pain relative to control= 1.476 ± 12.286

Treatment B mean +/- SD change in KOOS Pain relative to control= -0.391 ± 9.714

- Statistical test used to compare KOOS Pain and the p-values from it (separate p-values for Tx A and Tx B vs. control)
- T-test Treatment A P=0.5
- T-test Treatment B P=0.82

- Mean +/- SD *change* in KOOS Function separately for Treatment A and Treatment B from control (and # of subjects analyzed for each).
 - Statistical test used to compare KOOS Function and the p-values from it (separate p-values for Tx A and Tx B vs. control)

Treatment A mean +/- SD change in KOOS Function relative to control= 4.48 ± 12.56

Treatment B mean +/- SD change in KOOS Function relative to control= 0.64 ± 7.903

- T-test Treatment A P=0.05
- T-test Treatment B P=0.65

- Mean +/- SD *change* in KOOS Symptoms separately for Treatment A and Treatment B from control (and # of subjects analyzed for each).
- Treatment A mean +/- SD change in KOOS Symptoms relative to control= 3.571 ± 9.47
- Treatment B mean +/- SD change in KOOS Symptoms relative to control= -0.781 ± 10.876

- Statistical test used to compare KOOS Symptoms and the p-values from it (separate p-values for Tx A and Tx B vs. control)
- T-test Treatment A P=0.04
- T-test Treatment B P=0.68

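### With no stability rule at entry and rehabilitation unlogged, recovery can enter the before/after changes, and the SAP would read it as a treatment effect

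*Combined protocol and SAP*

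**What the plan says.** **Entry.** The Methods state: "Individuals with prior ACL injury/surgery, meniscus injury/surgery, and/or physician-diagnosed medial compartment knee osteoarthritis will be recruited". Osteoarthritis is therefore a separate route in, alongside injury or surgery. The only other stated condition on the participant is age: "The participants will be 18 years or older, and both males and females will be recruited". On screening, the text says "Subjects will be telephone screened for inclusion criteria" and mentions designated criteria, but lists no others. It gives no interval since injury or surgery, no stable-symptom requirement and no run-in.

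**Recruitment.** Participants may come through "direct referrals from clinicians in primary care, rheumatology, physical medicine and rehabilitation, physical therapy, radiology, and orthopedic surgery", and through flyers.

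**Co-treatment.** "During each treatment, subjects will maintain a daily wear log, pain diary, and medication usage". Rehabilitation, injections and procedures are neither restricted nor on this list.

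**Design and analysis.** "We will use a single-center, single-blind, randomized, crossover study design". Each participant has 4 weeks on one treatment, 2 weeks of washout and 4 weeks on the other: "For each subject, the trial will last for a total of 10 weeks". The Statistical Analysis Plan is one sentence. It applies paired two-tailed t-tests to "changes in patient-reported outcomes and joint loading parameters", each treatment against its pre-treatment value. It plans no comparison of A with B and no period term, and the Results section reports neither.

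**The concern.** A change measured against a person's own starting value isolates a treatment effect only if the condition would otherwise have stayed still. As the entry text reads, a person recently operated on, or partway through a course of physical therapy, is not excluded, and two of the six referral sources are places where such people are found. The Scientific Rationale itself counts physical therapy among the interventions used to improve strength, stability and pain, so this unrecorded co-treatment can move the outcomes being tested.

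The planned tests cannot tell that movement from an effect of the sleeve or the device. At stake is the meaning of each single-treatment p-value. Two of the printed results are borderline: Treatment A on KOOS Symptoms (P=0.04) and on KOOS Function (P=0.05).

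**Working it through.** The plan states no sample size, power, target effect or significance level, so there is no design figure to reproduce. The check has four steps.

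**1. Number analysed.** The Results give 38 at baseline but no number per treatment. It can be inferred from t = mean / (SD/√n) with n − 1 degrees of freedom:

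- Symptoms A, n = 32: 3.571 / (9.47/√32) = 3.571/1.674 = 2.13, p = 0.041 (printed 0.04).
- Function A, n = 32: 4.48 / (12.56/√32) = 4.48/2.220 = 2.02, p = 0.052 (printed 0.05).
- Function B, n = 32: 0.64 / (7.903/√32) = 0.64/1.397 = 0.46, p = 0.650 (printed 0.65).

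With n of 32 to 33, seven of the eight printed p-values reproduce within rounding. The exception is KFM for Treatment B (about 0.89 against a printed 0.64), which does not bear on this point. So n = 32 is an inference, not a stated figure.

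**2. Rejection rate under drift alone.** Suppose no treatment effect and a shared mean drift d over 4 weeks. The test statistic then follows a noncentral t with noncentrality d√n/SD. At n = 32 the two-sided 0.05 critical value is 2.040. The SDs are the largest and smallest printed for KOOS change, 12.56 (Function A) and 7.903 (Function B). The drift sizes are assumptions.

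| Drift (points) | Noncentrality, SD 12.56 | Rejection rate | Noncentrality, SD 7.903 | Rejection rate |
|---|---|---|---|---|
| 0 | 0 | 5% | 0 | 5% |
| 1 | 0.450 | 7.2% | 0.716 | 10.7% |
| 2.5 | 1.126 | 19.4% | 1.789 | 41.1% |
| 3 | 1.351 | 25.8% | 2.147 | 54.8% |

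At n = 38 the 2.5-point row would be 22% to 48%.

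**3. How much drift the printed results allow.** If Treatment B does nothing, its change estimates the shared drift. The 95% limits are mean ± 2.040 × SD/√32:

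- Pain: −0.391 ± 2.040 × 1.717 = −3.9 to 3.1
- Function: 0.64 ± 2.040 × 1.397 = −2.2 to 3.5
- Symptoms: −0.781 ± 2.040 × 1.923 = −4.7 to 3.1

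On that reading a drift of about 3 points is not excluded and a larger one is not supported. With n = 38 the upper limits would be 2.8, 3.2 and 2.8. For comparison, the lower 95% limit for Symptoms A at n = 32 is 3.571 − 2.040 × 1.674 = 0.16. Removing 1 point of drift would take it to about −0.84.

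**4. What the A-versus-B contrast does.** Let the drift be d1 in period 1 and d2 in period 2, and let τ be the true A − B difference. Participants taking A first have expected A − B difference τ + d1 − d2; those taking B first have τ + d2 − d1. The average over the two orders is τ, whether or not d1 equals d2. The printed means give A − B differences of:

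- Pain: 1.476 + 0.391 = 1.87
- Function: 4.48 − 0.64 = 3.84
- Symptoms: 3.571 + 0.781 = 4.35

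Their standard errors cannot be derived, because the within-subject correlation is not reported.

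**The case against.** The strongest reply is that nothing shows recovery took place. No passage says how many participants were recently injured, recently operated on or in therapy. Many may have entered through the osteoarthritis route. The screening criteria may be fuller than this short document shows. Pain and medication are logged, which captures part of any co-treatment. Treatment B's changes sit near zero. All of this stands. It limits the claim to what can happen under the plan, and it keeps the drift sizes as assumptions.

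Three stronger readings are tempting and are not supported:

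- **That Treatment A's gains are recovery.** A drift common to both treatments should also appear under B, and B shows none of any size. Drift masked by a harmful effect of B cannot be ruled out, but nothing in the documents points to it.
- **That a drift of 4 points or more is plausible.** The same formula would give 42-79% at 4 points, but that lies above all three upper limits for Treatment B.
- **That faster early recovery biases A against B.** Order is randomised, so a common trend falls on both treatments in expectation. It adds noise, which a period term can absorb. Bias would need unbalanced order left unadjusted, or a treatment-by-period interaction, and neither is shown. A gait test also appears to be taken at the start of the second period. If that is the control value for that period, earlier recovery does not accumulate.

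It is also fair to say that the exposure comes as much from the choice of contrast as from the entry rule. Screening alone would leave tests against zero open to placebo response and regression to the mean. That is why the analysis has to change as well.

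**Conclusion.** The concern holds in a limited form. The plan has no stability or time-since-injury rule, draws partly on rehabilitation and surgical clinics, does not log rehabilitation, and analyses only before/after change. Recovery or rehabilitation gain can therefore be counted as a treatment effect in any of the planned tests.

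For KOOS outcomes, modest shared drift of 1 to 3 points would lift the false-positive rate from 5% to somewhere between 7% and 55%, depending on drift and SD. This rests on about 32 analysed (inferred), a two-sided 0.05 level (assumed) and drift sizes that the documents neither give nor confirm. The upper end of 3 points further assumes that Treatment B itself has no effect. No size is worked out for KFM. The point is worth acting on, but it does not show that any printed result is false, and it does not undermine a randomised A-versus-B comparison.

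**What to change.** **For this dataset.** Results are already reported, so only records and analysis can help.

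- Extract time since injury or surgery, and any rehabilitation, injection or procedure during the 10 weeks.
- Report a sensitivity analysis without recent or actively rehabilitating cases. The clinical lead should set the windows before the outcomes are re-examined.
- Make the within-subject A − B difference with a period term the main comparison. Label it as added after results were available, and give the number analysed. The single-treatment changes can stay as description.

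**For any further enrolment.** Add to the telephone screen a question on stability since injury or surgery and one on recent change in knee treatment, with windows set by the clinical lead. Add rehabilitation to the daily log.

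**Cost.** Some record review and a short re-analysis now, with a smaller and less precise sample in the sensitivity analysis. For future enrolment, a protocol amendment, slightly slower recruitment and a somewhat narrower population.

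### No primary outcome, alpha or multiplicity control is set for an open list of tests, so the nominal sleeve changes in KOOS Symptoms and Function are not confirmatory

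*Combined protocol and SAP*

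**What the plan says.** The Statistical Analysis Plan reads "Paired two-tailed t-tests will be used to assess changes in patient-reported outcomes and joint loading parameters (e.g. peak knee flexion moment"), for each treatment against pre-treatment control. Nothing else in the document adds an alpha, a test order, a primary outcome or an adjustment.

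The other sections do not close the list:

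- The Focus paragraph gives the aim as the influence of device versus sleeve "on pain, function, and knee joint mechanics", without ranking the three.
- The Methods say "Subjects will be asked to complete questionnaires regarding pain, function, and physical activity". No instrument is named there; the KOOS subscales first appear under Results.
- On gait testing, "each subject may be asked to walk at a variety of speeds and perform activities of daily living". The number of speeds and activities is not given. KFM is reported for slow walking only.

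The Results print eight P-values. The three lowest all belong to Treatment A, which the Methods define as the control knee sleeve: KFM, "T-test Treatment A P=0.005"; KOOS Function, "T-test Treatment A P=0.05"; KOOS Symptoms, "T-test Treatment A P=0.04". The Treatment B (device) P-values are 0.64, 0.82, 0.65 and 0.68.

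**The concern.** A plan that tests every outcome for each treatment, with none designated primary, lets any result below 0.05 be quoted afterwards as if it had been the one in view. With eight tests the chance of at least one such result under no true change is well above 5%. It grows with each further parameter, speed or questionnaire that the open wording admits.

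The printed record shows where this bites. Symptoms is not among the domains that the Methods say the questionnaires will cover, yet KOOS Symptoms on the sleeve is the only KOOS P-value printed below 0.05. Physical activity is among those domains but has no printed result. KFM appears for one walking speed, and no text before the Results singles out that speed. A reader of the public record could take 0.04 and 0.05 as findings that the sleeve improves symptoms and function.

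**Working it through.** **Inputs.** The eight P-values, means and SDs come from the Results. Alpha is not stated; two-sided 0.05 is assumed, since the plan says only "Paired two-tailed t-tests will be used". The number analysed per treatment is not given; 38 is the baseline number.

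**1. Reproducing the printed P-values.** Use t = mean change / (SD/√n), df = n − 1, two-sided.

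| Treatment A outcome | Mean ± SD | Printed P | P at n=32 | P at n=33 | P at n=38 |
|---|---|---|---|---|---|
| KFM | 0.197 ± 0.374 | 0.005 | 0.0056 | 0.0049 | 0.0025 |
| KOOS Pain | 1.476 ± 12.286 | 0.5 | 0.502 | 0.495 | 0.464 |
| KOOS Function | 4.48 ± 12.56 | 0.05 | 0.0523 | 0.0487 | 0.0342 |
| KOOS Symptoms | 3.571 ± 9.47 | 0.04 | 0.0409 | 0.0379 | 0.0257 |

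An n of 33 reproduces all four; 38 does not. The n is therefore inferred, not documented. Function lies on either side of 0.05 depending on whether n is 32 or 33, before any adjustment.

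**2. Chance of at least one false positive in eight tests at 0.05.**

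- Independent tests: 1 − 0.95^8 = 0.337.
- Four outcomes correlated within a treatment, the two treatments independent (simulated z-tests): 0.32, 0.29 and 0.24 at correlations of 0.3, 0.5 and 0.7.
- The design is a crossover, so the same subjects supply both treatments and cross-treatment correlation is likely. With 0.7 within and 0.5 across: 0.22. With 0.7 throughout: 0.19.

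The correlations are assumed; the document gives none. Under them the range is about 19–32%, roughly four to six times 5%.

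**3. Holm adjustment of the eight printed P-values.**

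- KFM A: 0.005 × 8 = 0.040
- KOOS Symptoms A: 0.04 × 7 = 0.28
- KOOS Function A: 0.05 × 6 = 0.30
- Next smallest, KOOS Pain A: 0.5 × 5 > 1, so it and all others are 1

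**4. Does the KOOS result depend on the family chosen?** Holm values must not decrease down the ordered list, so a smaller product is raised to the one before it.

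| Family | Symptoms A | Function A |
|---|---|---|
| 6 KOOS tests | 0.04 × 6 = 0.24 | 0.05 × 5 = 0.25 |
| 4 Treatment A tests | 0.04 × 3 = 0.12 | 0.05 × 2 = 0.10, raised to 0.12 |
| 3 Treatment A KOOS tests | 0.04 × 3 = 0.12 | 0.05 × 2 = 0.10, raised to 0.12 |
| 8 tests, P recomputed at n=38 | 0.0257 × 7 = 0.18 | 0.0342 × 6 = 0.21 |

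Neither reaches 0.05 in any of these, including n=38, the most favourable case.

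**5. How firm is KFM A?** Allowing for rounding of 0.005 (0.0045 to 0.0055), eight tests give 0.036 to 0.044, so it holds. Each further parameter or speed is tested for both treatments and so adds two tests. One more gives 10 tests and 0.005 × 10 = 0.050; two more give 12 tests and 0.005 × 12 = 0.060. The document does not say whether any were run.

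**The case against.** The strongest reply is that nothing about the device is at stake. The Purpose and Focus concern the cutaneous stimulation device, its four P-values run from 0.64 to 0.82, and no adjustment alters them. The only low P-values are pre-post changes on the comparator. That stands, and it limits the consequence.

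It can also be said that the document claims no significance in words and emphasises no P-value; the Results read like completed reporting prompts. Function is printed as exactly 0.05, not below it. That stands too, and it means the point concerns how the printed values may be read rather than a stated conclusion.

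Two stronger readings are tempting and should be resisted:

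- A reader might infer selective reporting from the single walking speed, the unannounced Symptoms subscale and the missing physical activity result. The document does not show that other tests were run and withheld. It shows only that the plan could not rule this out.
- A reader might propose repairing the plan by naming KOOS Pain as primary, since pain comes first in the title and the Focus and its P-values (0.5 and 0.82) bring no advantage. A choice made with those values in hand is still data-driven and cannot restore pre-specification. The support is also thin: the Methods plan a pain diary as well, and the only outcome the plan itself names is KFM.

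What the reply does not answer is that eight unranked, unadjusted tests are on record, with two sleeve KOOS results at or just below 0.05.

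**Conclusion.** The point holds at should-fix severity. With alpha taken as two-sided 0.05, following the plan as written carries a chance of at least one false positive of 34% under independence and about 19–32% under the correlations assumed above.

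After Holm over the eight printed tests, KOOS Symptoms A (0.28) and KOOS Function A (0.30) are not significant. That does not depend on the families tried or on an analysed n between 32 and 38. KFM A (0.040) survives the eight printed tests, but on the printed P-value it would not survive 12.

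The adjusted values do not show that the sleeve has no effect on symptoms or function; they show that these results cannot be read as confirmatory. Nor do they show that a P of 0.04 could never have counted: a single primary outcome or a test hierarchy fixed in advance might have supported it. The defect is the lack of pre-specification.

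Three matters are separate: the missing analysed n; the absence of a planned sleeve-versus-device test; and the printed KFM P-value for Treatment B (0.64), where 0.018 ± 0.725 gives about 0.88 to 0.89 at n = 32 to 38. The last does not affect the Holm results, because that test adjusts to 1 either way.

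**What to change.** - Close the list: state every outcome, walking speed, activity and loading parameter tested for each treatment, including those not printed.
- Name a primary outcome only if a document dated before the data were seen does so, and cite it. Otherwise state that none was pre-specified and label all tests exploratory. Do not designate KOOS Pain, or any other outcome, after the fact.
- State the alpha, and print raw and Holm-adjusted P-values side by side, with Holm taken over all tests actually run.
- State that no KOOS change is significant after adjustment.

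The cost is about two sentences and one column in the results table, with no new data. KOOS Symptoms and Function on the sleeve will show less favourable P-values. If further gait tests were run, the KFM result on the sleeve may do so too.

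### The SAP scores outcomes only as raw change from pre-treatment; a device-versus-sleeve contrast should use end-of-treatment values with period baselines as covariates, for a gain that depends on an unreported correlation

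*Combined protocol and SAP*

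**What the plan says.** The Focus paragraph says that "this study aims to assess the influence of the cutaneous stimulation device versus a commercially-available knee sleeve on pain, function, and knee joint mechanics". Methods describes a "single-center, single-blind, randomized, crossover study design".

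The schedule in Methods has four weeks on one treatment, two weeks without treatment, then four weeks on the other. Gait is tested at the start and end of the first period. The second treatment is then "assigned for a 4-week period and a gait test performed", with another gait test when that period ends. Start-of-period gait values are therefore planned at weeks 0 and 6, and end-of-period values at weeks 4 and 10. Questionnaires are mentioned, but the visits at which they are completed are not stated.

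The Statistical Analysis Plan is one sentence, which plans paired two-sided t-tests of "changes in patient-reported outcomes and joint loading parameters (e.g. peak knee flexion moment) with each treatment from pre-treatment control". It does not say whether that reference is each period's own baseline or one week-0 value. It names no baseline covariate and no device-versus-sleeve test.

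The Results section follows the same pattern, for example "Treatment A mean +/- SD change in KOOS Pain relative to control= 1.476 ± 12.286". Sleeve (A) and device (B) are tested separately, and one baseline mean and SD is printed per outcome.

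**The concern.** In a crossover each subject already serves as their own control, so the natural quantity for the stated aim is the within-subject difference between the two end-of-treatment values. If each end value first has its own period's baseline subtracted, two further measurements, with their errors, enter the difference. Subtraction fixes the baseline coefficient at 1, whereas a covariate lets the data choose it.

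The change from pre-treatment is the only scale the SAP defines, so anyone adding the missing device-sleeve comparison would probably build it on that scale. Baseline values exist for 38 subjects, and the printed P-values suggest that about 32 to 34 were analysed. In a trial of that size, needless variance widens the interval for the comparison the trial was run to make, and a real difference is more easily missed.

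**Working it through.** There is no planned device-sleeve figure to reproduce, so this is a comparison of variances.

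**Notation.** D is the device-minus-sleeve difference in end-of-treatment values and V its variance. X is the matching difference in start-of-period values, assumed also to have variance V. r is the correlation of X and D.

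**Case 1: each period's own baseline is the reference.**
- Difference of changes: Var(D-X) = V + V - 2rV = 2(1-r)V.
- D adjusted for X: (1-r²)V.
- Ratio: (1-r²)/[2(1-r)] = (1+r)/2, so the reduction is (1-r)/2.

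**Case 2: one week-0 value is the reference for both treatments.** The baseline cancels: (Y_B - X₀) - (Y_A - X₀) = Y_B - Y_A, with variance V. Adjusting for X, which needs a week-6 value, gives (1-r²)V, a reduction of r².

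**Cost of estimating the slope.** With n=32 and terms for intercept, sequence and slope, the adjusted variance is multiplied by about 1 + 1/(32-4) = 1.036. A simulation at n=32 agreed with the net figures below to within half a percentage point or so.

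| r | Case 1, large sample | Case 1, n=32 | Case 2, large sample | Case 2, n=32 |
|---|---|---|---|---|
| 0 | 50% | 48% | 0% | -4% |
| 0.4 | 30% | 28% | 16% | 13% |
| 0.6 | 20% | 17% | 36% | 34% |
| 0.8 | 10% | 7% | 64% | 63% |

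**What the documents say about r.** They give neither r nor any between-period correlation. The printed SDs give only a rough within-period correlation, ρw = 1 - SD_change²/(2·SD_baseline²), assuming equal SDs before and after treatment. For KOOS Pain under A this is 1 - 12.286²/(2×13.4²) = 1 - 150.95/359.12 = 0.58. If the between-period correlation is a common value ρb, then r = (ρw - ρb)/(1 - ρb). A case 1 reduction of at least 20% needs r ≤ 0.6, that is ρb ≥ (ρw - 0.6)/0.4.

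| Outcome | ρw under A | ρw under B | ρb needed, from A | ρb needed, from B |
|---|---|---|---|---|
| Knee flexion moment | 0.96 | 0.85 | 0.90 | 0.62 |
| KOOS Pain | 0.58 | 0.74 | any | 0.34 |
| KOOS Function | 0.69 | 0.88 | 0.23 | 0.69 |
| KOOS Symptoms | 0.82 | 0.76 | 0.54 | 0.39 |

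For the knee flexion moment, ρw = 0.96 with an assumed ρb of 0.8 gives r = 0.16/0.20 = 0.8 and a case 1 reduction of 10%. With ρb = 0.7, r = 0.87 and the reduction is 7%. The value under B needs caution: a change of 0.018 ± 0.725 gives P of about 0.89 at n=32, not the printed 0.64. Under a different assumption, serial correlation decaying over weeks 0, 4, 6 and 10 (0.7 to 0.99 per week), r runs from -0.02 to 0.31 and the case 1 reduction from 51% to 34%.

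**Illustration in KOOS points (case 1, n=32, the two change scores assumed uncorrelated).** Pain: SD = √(12.286² + 9.714²) = 15.66, and the 95% half-width is 2.04×15.66/√32 = 5.65. Multiplying by √[(1+r)/2], before the slope cost:

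| Scale | Difference of changes | Adjusted, r=0 | r=0.6 | r=0.8 |
|---|---|---|---|---|
| Pain | 5.65 | 3.99 | 5.05 | 5.36 |
| Function | 5.35 | 3.78 | 4.79 | 5.08 |
| Symptoms | 5.20 | 3.68 | 4.65 | 4.93 |

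**The case against.** A reader might infer that the SAP's scoring already adds baseline noise to the trial's device-sleeve result, and that baseline covariates would remove 20% to 50% of its variance. The documents do not support that.

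- No device-sleeve difference is planned or reported, so there is no estimate for the noise to enter. For the within-treatment change that is planned, subtracting the pre-treatment value is what defines the quantity. The missing comparison is the larger defect. This stands.
- The added noise requires period-specific baselines. The SAP does not define its reference, and a single printed baseline per outcome fits one week-0 value at least as well. This stands, but it does not remove the case for the covariate, which then gains about r² if week-6 values exist.
- The range of 20% to 50% is simply r from 0.6 to 0, which the documents cannot confirm. At r=0 the covariate explains nothing, and the whole gain comes from not subtracting. This stands.
- The knee flexion moment, the SAP's own example and an outcome with documented start-of-period tests, may gain least under period-specific baselines. This stands.
- A week-6 KOOS measurement is not documented, so covariate adjustment for KOOS may not be possible. This stands until the questionnaire visits are stated.

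What survives is that the SAP's only scale is a poor base for the comparison the trial set out to make, and that the better analysis uses gait data already scheduled.

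**Conclusion.** The point holds conditionally, as an improvement to make when the device-sleeve comparison is added. Against a difference of period-specific changes, adjustment reduces variance by (1-r)/2: up to about 50% at r=0, 20% at r=0.6 and 10% at r=0.8, and about 48%, 17% and 7% at n=32. Against a shared week-0 reference, subtraction does no harm; the week-6 covariate gains about r², with a loss of about 4% at r=0.

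This rests on equal variances of the baseline and end-value differences, on an r that the documents do not give, and on an analysed number inferred from the P-values. Gains above 20% are plausible for the KOOS scales if their period baselines exist. For the knee flexion moment with period-specific baselines, the gain may be about 10% or less.

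**What to change.** Amend the Statistical Analysis Plan as follows.

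- Add a device-versus-sleeve comparison for each outcome, based on end-of-treatment values at weeks 4 and 10.
- Analyse the within-subject device-minus-sleeve difference with a period (sequence) term and the matching week-0/week-6 baseline difference as covariate, or use the equivalent mixed model. Without the period term, unequal sequence sizes would mix a period effect into the treatment estimate.
- Apply the covariate to gait outcomes. Apply it to KOOS only if KOOS is recorded at week 6, and state the questionnaire visits. Otherwise compare KOOS end values with the period term alone.
- Define the pre-treatment reference for each treatment.
- Keep the within-treatment changes as descriptive summaries.

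The cost is SAP wording, one extra model per outcome and about one degree of freedom for the slope. Gait outcomes need no extra visits or subjects. Because results are already printed in this document, the added analysis should be labelled as specified after they were known.
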